7 STUDY INTERVENTION DISCONTINUATION AND PARTICIPANT DISCONTINUATION/WITHDRAWAL

7.1 DISCONTINUATION OF STUDY INTERVENTION

Discontinuation from porcine xenograft placement does not mean discontinuation from the study, and remaining study procedures should be completed as indicated by the study protocol. If a clinically significant finding is identified (including, but not limited to changes from baseline) after enrollment, the investigator or qualified designee will determine if any change in participant management is needed. Any new clinically relevant finding will be reported as an adverse event (AE).

The data to be collected at the time of study intervention discontinuation will include the following:

- Reason for discontinuation
- Specific complications
- Scar size
- Pain score

7.2 PARTICIPANT DISCONTINUATION/WITHDRAWAL FROM THE STUDY

If patients decide to withdraw from the study, there is no danger involved with early withdrawal. Patients will be advised to follow up with the surgeon as normal standard of care outside the research setting.

Should patients wish to have their porcine xenograft removed following enrollment in the porcine xenograft arm or suffer from other complications resulting in porcine xenograft failure, they will be assessed in an intention to treat method.

7.3 LOST TO FOLLOW-UP

If patients fail to show up for the follow-up visit, they will be withdrawn from the study. An evaluable patient will be one who completes the final 3 month follow -up office visit.

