8.4.3 REPORTING UNANTICIPATED PROBLEMS TO PARTICIPANTS N/A

9 STATISTICAL CONSIDERATIONS

9.1 STATISTICAL HYPOTHESES

• **Primary Efficacy Endpoint(s):** The primary efficacy endpoint is the **POSAS observer scale total score**, evaluated at the 3-month follow-up visit (detailed in Section 9.4.2). The Mann-Whitney U test will be used to assess the superiority of porcine xenograft to second intention healing with respect to this endpoint. A two-sided hypothesis test will be used.

 H_0 : The distributions of POSAS observer scale total score are equal for patients treated with porcine xenograft and second intention healing. H_1 : The distributions of POSAS observer scale total score are not equal for patients treated with porcine xenograft and second intention healing.

- Secondary Efficacy Endpoint(s): The Mann Whitney U test will be used to assess the superiority of porcine xenograft to second intention healing for each of the secondary endpoints below. Additional details for each endpoint are provided in Section 9.4.3. Two-sided hypothesis tests will be used.
- 1. **POSAS patient scale total score**, evaluated at the 3-month follow-up visit by study participants.
- 2. **Healing time**, measured in weeks based on patient's responses to question 1 of the weekly follow-up questionnaire.
- 3. Ratio of scare size to initial defect size
- 4. Pain score at 1 week following surgery
- 5. Number of weeks with pain score above 1

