9.3 POPULATIONS FOR ANALYSES

A modified intention to treat analysis will be performed. All patients will be analyzed according to randomized treatment assignment, unless a patient prefers an alternative treatment method between the time he/she is randomized and the procedure (in which case the patient will be excluded from the study). The **Modified Intention-to-Treat (mITT) Population** will consist of all patients who receive the study intervention and show up for the 3-month office visit follow-up, during which the primary endpoint is evaluated. The Modified Intention-to Treat Population will also include patients who required the rescue therapy, and had the primary endpoint assessed at a follow-up visit when the wound had completely healed. This population will be used to analyze the primary endpoint and all secondary endpoints.

The **Safety Population** will consist of all patients who receive the randomized study intervention. This population will be used to analyze all safety endpoints.

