The POSAS patient scale, healing time, and number of weeks with pain score above 1 are all subjective endpoints. The ratio of scar size to initial defect size is an objective endpoints.

Statistical Analysis: The Mann Whitney U test will be used to compare the two study arms on each of the secondary endpoints based on the mITT Population defined in Section 9.3.

We will summarize each secondary endpoint for the two study arms using the mean (SD), and median (IQR). As a measure of effect size between the porcine xenograft and second intention healing groups, we will calculate the Hodges-Lehmann estimate of the median difference, and corresponding 95% confidence interval. This is equal to the median of all paired differences between observations in the porcine xenograft and second intention healing groups.

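### Efficacy analyses are limited to patients who attend the 3-month visit, so week-1 pain and other questionnaire data already collected from non-attenders are discarded, and missing POSAS scores get no sensitivity analysis

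*Combined protocol and SAP*

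**What the plan says.** Section 7.3 sets the rule for no-shows: "If patients fail to show up for the follow-up visit, they will be withdrawn from the study". It adds that "An evaluable patient will be one who completes the final 3 month follow -up office visit".

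Section 9.3 defines the mITT population as "all patients who receive the study intervention and show up for the 3-month office visit follow-up, during which the primary endpoint is evaluated". The one exception covers "patients who required the rescue therapy, and had the primary endpoint assessed at a follow-up visit when the wound had completely healed". Of the mITT population it says: "This population will be used to analyze the primary endpoint and all secondary endpoints". Section 9.4.3 repeats this for the Mann-Whitney tests, which "compare the two study arms on each of the secondary endpoints based on the mITT Population defined in Section 9.3".

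Other parts of the document bear on the point:

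- Section 8.1 has the weekly questionnaires delivered by phone or email up to week 12. Section 9.4.3 takes healing time and both pain endpoints, including "Pain score at 1 week following surgery", from them.
- The Safety Population in Section 9.3 requires only that the randomized intervention was received. Section 9.4.4 uses it for a yes/no endpoint built on the same week-1 pain answer.
- Section 9.2 allows for 10% attrition by recruiting 50 patients.
- Section 9 gives no missing-data rule, imputation or sensitivity analysis. Sections 9.4.7 and 9.4.9 are marked not applicable.

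**The concern.** Attendance at 3 months happens after randomization. Patients know their treatment (Section 4.1), and POSAS cannot be scored on an open wound (Section 6.5.1). Whether a score exists may therefore depend on both arm and outcome, and a comparison of attenders alone may be biased. Recruiting extra patients protects power but does nothing about bias.

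For the questionnaire endpoints the exclusion has no evident purpose. Section 9.3 ties the visit condition to the fact that patients "show up for the 3-month office visit follow-up, during which the primary endpoint is evaluated", which is a reason for POSAS but not for a pain score given by phone at week 1. The plan is also uneven: the same week-1 answer from the same non-attender counts for safety and is dropped for efficacy.

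**Working it through.** **1. The plan's own figures.** Inputs from Section 9.2: difference 6, SD 6.5, two-sided alpha 0.05, power 80%, ARE 0.864, attrition 10%.

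- Per arm, normal approximation: 2 × (1.960 + 0.842)² × (6.5/6)² = 18.4, so 19 per arm and 38 in total. The exact t calculation gives 79.1% power at 38, close to the stated 80%.
- 38 / 0.864 = 43.98, so 44.
- 44 / 0.90 = 48.9, so 49, made even for 1:1 allocation: 50.
- With 50 × 0.90 = 45 completers, the ARE-equivalent t-test size is 45 × 0.864 = 38.9, and power is 80.0%.

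The sample size chain reproduces and is not at fault. Expected losses are 50 × 0.10 = 5 patients.

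**2. Which endpoints need the visit.**

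| Endpoint | Source | Needs the 3-month visit? | Population |
|---|---|---|---|
| POSAS observer score | visit | yes | mITT |
| POSAS patient score | visit | yes | mITT |
| Scar-to-defect ratio | visit | yes | mITT |
| Week-1 pain score | questionnaire | no | mITT |
| Weeks with pain above 1 | questionnaires | no | mITT |
| Healing time | questionnaires | no | mITT |
| High week-1 pain (safety, yes/no) | questionnaire | no | Safety |

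**3. Precision for week-1 pain.** The confidence interval half-width is t × SD × √(1/n₁ + 1/n₂). With SD 6.5 as a scale:

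- 45 patients (22 and 23): 2.017 × 6.5 × 0.298 = 3.91.
- 50 patients (25 and 25): 2.011 × 6.5 × 0.283 = 3.70.
- Narrowing: (3.91 − 3.70) / 3.91 ≈ 5%.

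The documents give no SD for pain, but the percentage does not depend on it. It is an upper limit, because it assumes that all 5 non-attenders answered at week 1.

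**4. Bias in POSAS.** The documents do not say how losses would arise, so the patterns below are assumptions. Simulation: 25 per arm, normal, SD 6.5, no true difference, two-sided Mann-Whitney test on completers. Graded loss means that the chance of being missing doubles for each SD of worse score, in one arm only.

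| Loss pattern | Mean false difference | Rejection rate |
|---|---|---|
| Random | none | about 5% |
| Graded in one arm, 3 vs 2 or 4 vs 1 | about 0.6 to 0.7 points | about 6% |
| 3 worst in one arm, 2 random in the other | 1.4 points | 11 to 12% |
| 4 worst in one arm, 1 random in the other | 1.8 points | 15% |

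The arm that loses its worst scars looks better than it is. The same can be seen directly. Take a completer difference of −6 and assume lost patients score 6 points worse than completers in their own arm. If all 5 losses are in the xenograft arm, the difference in all 50 is −6 + (5/25) × 6 = −4.8. If 3 are lost from xenograft and 2 from control, it is −6 + (3/25 − 2/25) × 6 = −5.76.

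**5. Worst-rank scoring as a remedy.** Under the same model, with every missing score given the worst rank and losses purely random:

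| Losses, xenograft vs control | Power at a true 6 points |
|---|---|
| 2 vs 3 | about 82% |
| 3 vs 2 | about 63% |
| 4 vs 1 | about 36% |

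Completer power is about 83 to 84% for the first two splits. With no true effect, worst-rank scoring rejects about 8% of the time at 4 vs 1 and 20% at 5 vs 0. Best-rank scoring rejects about 30% when the 4 worst scars in one arm and 1 random patient in the other are missing.

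**The case against.** Several points on the other side stand.

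- **Safety is not affected by the rule.** A reader might infer that no-shows vanish from every analysis. The Safety Population has no visit condition, so the point concerns efficacy only.
- **Losses are already being limited.** The visit window is ±1 month, contact details are kept for call-back, and rescue patients scored later, once healed, stay in mITT. These steps may reduce the number of missing scores; they do not change how the remaining ones are handled.
- **A false-positive rate near 15% might be inferred.** It needs one arm to lose exactly its worst scars. Nothing in the documents suggests this, and graded loss gives about 6%.
- **Unhealed patients might be thought excluded from mITT by definition.** For ordinary attenders, Section 9.3 asks for attendance, not healing. The obstacle is that an open wound cannot be scored.
- **Moving the questionnaire endpoints is not wholly free.** Only week-1 pain moves cleanly. A patient who stops answering early would get too low a count of painful weeks, and might have no healing time to rank. Having answered is itself a post-randomization condition, so responders are not identical to the Safety Population.
- **Secondary endpoints are declared exploratory** in Section 9.4.3. That lowers the stakes but gives no reason to discard collected data.

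**Conclusion.** The point holds as a defect in the definition of the efficacy population. It is an explicit rule, not merely silence, and for week-1 pain it discards usable data for no benefit. Up to 5 of 50 patients are affected at the planned attrition, with a precision gain of at most about 5%. No bias has been quantified for the questionnaire endpoints.

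For POSAS, mITT is a workable primary population, since a score that was never taken cannot be analysed directly. What is missing is a prespecified check. The possible bias runs from none to 1.8 points across the patterns with 5 losses tabulated above, against an assumed effect of 6. These figures rest on assumed loss patterns, normal scores and SD 6.5; they show possible size and do not predict it.

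The documents do not support reading this as a sample size error, or as grounds for replacing the primary analysis with worst-rank scoring.

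**What to change.** In Section 9.3, with matching edits to 7.3 and 9.4.3:

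1. **Week-1 pain score.** Analyse it in all patients who received the randomized intervention and answered the week-1 questionnaire, whether or not they attended at 3 months.
2. **Healing time and weeks in pain.** Do the same, with a stated rule for incomplete questionnaires. For example, censor healing time at the last questionnaire answered and compare arms by log-rank, and express weeks in pain as a proportion of questionnaires answered.
3. **POSAS observer score.** Keep mITT as primary. Add a prespecified sensitivity analysis for missing scores, for example multiple imputation with a tipping-point shift by arm, and report missing scores by arm and reason.
4. **Never-healed wounds.** Treat them separately from no-shows. The worst rank is reasonable for a wound that never healed; the best rank is not. For no-shows, worst and best rank serve only as stress bounds.

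Cost: item 1 needs no new data and only a change of wording. Item 2 needs the partial-data rules and a change of test for healing time. Items 3 and 4 need modest extra programming, fixed before treatment codes are known. Worst-rank scoring can lose much power and can reject falsely when losses are unbalanced, so it must not replace the primary analysis.

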8 STUDY ASSESSMENTS AND PROCEDURES

8.1 EFFICACY ASSESSMENTS

The authors will conduct a comparative two-arm study investigating outcomes of second intention healing versus porcine xenograft placement of post-operative Mohs surgery or excision wound defects.

This will be a randomized evaluator blinded study with a prior power analysis. Basic demographic data will be obtained including date of birth, sex, and race. Medical record number will be retained to obtain phone number or address for patient call back should patient not show for their follow-up appointments.

Surgical defects 8 mm in diameter or larger on the lower extremities will be eligible for enrollment. Only patients with one wound will be eligible for enrollment. Primary intention (also known as linear layered) repair is not feasible in many patients with defects on the foot, ankle, or distal extremity as these are sites under high tension and poor circulation. Patients with small post-op defects many also opt not to be sutured via primary intention to avoid physical activity restrictions due to the increased risk of wound dehiscence. When closed via primary intention, a 0.8cm defect results in a scar of greater than or equal to 2.4cm.

Patients will be randomized to either receive a porcine xenograft or allow the wound to granulate via second intention. If primary/linear repair is not an acceptable option, the standard of care at Northwell is to allow the wound to heal on its own via second intention post-operatively. Due to recently published retrospective studies, there is a suggestion that porcine xenografts may be a feasible alternative to second intent healing. Currently, it is the surgeon's (and patient's) choice, after a discussion of risks and benefits of each modality, what is done.

Prior to intervention the defect size will be measured in terms of length and width using a sterile ruler.

After procedure completion wound care instruction will include daily dressing changes and application of petroleum jelly using a cotton tipped applicator to the wound daily until it is healed.

Weekly questionnaires will be given to the patients by phone or email follow-up until 12 weeks postsurgery.

The mode of treatment for participants will remain consistent throughout the 3-month period, as both methods are reliable for this type of defect. It is not general practice to place a xenograft on a wound healing by second intention or to remove a xenograft after one has been placed to switch to second intention. Should there be any complications, a modified intention to treat principle, described in Section 9, will be adhered to.

The scars for both study groups will be measured at a single follow up visit after 3 months ± 1 month, and two blinded investigators will then assess the scar at this time. The blinded evaluators will be other MDs not involved in the study who are working in the dermatology department. The Principle Investigator will speak with the physician to outline what needs to be recorded for each patient. The validated physician observer scar assessment instrument (POSAS) will be used for this purpose. Scar size will consist of a length x width measurement using a ruler.

The research team consists of one physician who will perform all of the surgical procedures, which will remove bias in technique.>

8.2 SAFETY AND OTHER ASSESSMENTS

NIH-FDA Clinical Trial Protocol Template - v1.0 7 Apr 2017 Northwell Version: 9/16/2019

Each patient will undergo examination of the surgical defect. Any adverse effects will be recorded. Formal safety endpoints are described in Section 9.4.4. Standard protocol for porcine xenograft placement and secondary intention will be followed.

8.3 ADVERSE EVENTS AND SERIOUS ADVERSE EVENTS

8.3.1 DEFINITION OF ADVERSE EVENTS (AE)

Adverse event means any untoward medical occurrence associated with the use of an intervention in humans, whether or not considered intervention-related (21 CFR 312.32 (a)).

8.3.2 DEFINITION OF SERIOUS ADVERSE EVENTS (SAE)

Adverse events (AE) or suspected adverse reactions in dermatologic surgery are associated with postoperative hemorrhage and hematoma formation, graft necrosis, flap necrosis, postoperative infection, and wound dehiscence. However, the rate of complications is low at 1.6%. Important medical events that may not result in death, be life-threatening, or require hospitalization may be considered serious when, based upon appropriate medical judgment, they may jeopardize the participant and may require medical or surgical intervention to prevent one of the outcomes listed in this definition.

8.3.3 CLASSIFICATION OF AN ADVERSE EVENT

8.3.3.1 SEVERITY OF EVENT

For adverse events (AEs) not included in the protocol defined grading system, the following guidelines will be used to describe severity.

- **Mild** Events require minimal or no treatment and do not interfere with the participant's daily activities.
- **Moderate** Events result in a low level of inconvenience or concern with the therapeutic measures. Moderate events may cause some interference with functioning.
- Severe Events interrupt a participant's usual daily activity and may require systemic drug therapy or other treatment. Severe events are usually potentially life-threatening or incapacitating. Of note, the term "severe" does not necessarily equate to "serious".

8.3.3.2 RELATIONSHIP TO STUDY INTERVENTION

• Definitely Related – There is clear evidence to suggest a causal relationship, and other possible contributing factors can be ruled out. The clinical event, including an abnormal laboratory test result, occurs in a plausible time relationship to study intervention administration and cannot be explained by concurrent disease or other drugs or chemicals. The response to withdrawal of the study intervention (dechallenge) should be clinically plausible. The event must be pharmacologically or phenomenologically definitive, with use of a satisfactory rechallenge procedure if necessary.

• Probably Related – There is evidence to suggest a causal relationship, and the influence of other factors is unlikely. The clinical event, including an abnormal laboratory test result, occurs within a reasonable time after administration of the study intervention, is unlikely to be attributed to concurrent disease or other drugs or chemicals, and follows a clinically reasonable response on withdrawal (dechallenge). Rechallenge information is not required to fulfill this definition.

• Potentially Related – There is some evidence to suggest a causal relationship (e.g., the event occurred within a reasonable time after administration of the trial medication). However, other factors may have contributed to the event (e.g., the participant's clinical condition, other concomitant events). Although an AE may rate only as "possibly related" soon after discovery, it can be flagged as requiring more information and later be upgraded to "probably related" or "definitely related", as appropriate.

• Unlikely to be related – A clinical event, including an abnormal laboratory test result, whose temporal relationship to study intervention administration makes a causal relationship improbable (e.g., the event did not occur within a reasonable time after administration of the study intervention) and in which other drugs or chemicals or underlying disease provides plausible explanations (e.g., the participant's clinical condition, other concomitant treatments).

• Not Related – The AE is completely independent of study intervention administration, and/or evidence exists that the event is definitely related to another etiology. There must be an alternative, definitive etiology documented by the clinician.

8.3.3.3 EXPECTEDNESS

[name], MD will be responsible for determining whether an adverse event (AE) is expected or unexpected. An AE will be considered unexpected if the nature, severity, or frequency of the event is not consistent with the risk information previously described for the study intervention.

8.3.4 TIME PERIOD AND FREQUENCY FOR EVENT ASSESSMENT AND FOLLOW-UP

The occurrence of an adverse event (AE) or serious adverse event (SAE) may come to the attention of study personnel during study visits and interviews of a study participant presenting for medical care, or upon review by a study monitor.

All AEs including local and systemic reactions not meeting the criteria for SAEs will be captured on the appropriate case report form (CRF). Information to be collected includes event description, time of onset, clinician's assessment of severity, relationship to study product (assessed only by those with the training and authority to make a diagnosis), and time of resolution/stabilization of the event. All AEs occurring while on study must be documented appropriately regardless of relationship. All AEs will be followed to adequate resolution.

Any medical condition that is present at the time that the participant is screened will be considered as baseline and not reported as an AE. However, if the study participant's condition deteriorates at any time during the study, it will be recorded as an AE.

Changes in the severity of an AE will be documented to allow an assessment of the duration of the event at each level of severity to be performed. AEs characterized as intermittent require documentation of onset and duration of each episode.

[name] will record all reportable events with start dates occurring any time after informed consent is obtained until 7 (for non-serious AEs) or 30 days (for SAEs) after the last day of study participation. At each study visit, the investigator will inquire about the occurrence of AE/SAEs since the last visit. Events will be followed for outcome information until resolution or stabilization.

